7.2.5 Safety analyses

Adverse events will be coded using the current version of Medical Dictionary for Regulatory Activities (MedDRA) coding dictionary. Standard Boehringer Ingelheim's summary tables and listings will be produced.

All randomized and treated patients will be included in the safety analysis. In general, safety analyses will be descriptive in nature and will be based on BI standards. No hypothesis testing is planned. Statistical analysis and reporting of adverse events will concentrate on treatment-emergent adverse events (TEAE). To this end, all adverse events occurring between start of treatment and end of the residual effect period will be considered 'treatment-emergent'; the residual effect period (REP) is defined as 16 weeks after the last dose of trial medication. Adverse events that start before first drug intake and deteriorate under treatment will also be considered as 'treatment-emergent'.

Frequency, severity, and causal relationship of adverse events will be tabulated by system organ class (SOC) and preferred term after coding according to the current version of the MedDRA at database lock.

Laboratory data will be analysed both quantitatively as well as qualitatively. The later will be done via comparison of laboratory data to their reference ranges. Values outside the reference range as well as values defined as clinically relevant will be highlighted in the listings. Treatment groups will be compared descriptively with regard to distribution parameters as well as with regard to frequency and percentage of patients with abnormal values or clinically relevant abnormal values. Vital signs, physical examinations, or other safety-relevant data observed at screening, baseline, during the course of the trial and at the end-of-trial evaluation will be assessed with regard to possible changes compared to findings before start of treatment.

Immunogenicity data will be analysed in a descriptive way.

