A2.19	Previous enrolment in this trial except for patients re-screened. LABEL: Previous enrolment in this trial except for patients re-screened	EC19	PPS
B	Informed consent		
B1	Informed consent not available LABEL: No IC form	IC02 Date of informed consent missing or no signature on patient's "Declaration of Informed Consent" In this case: Patient's data will not be used at all.	All
B2	Informed consent too late LABEL: IC too late.	IC02 Informed consent date was after Visit 1	None
C	Trial medication and randomisation		
C1	Incorrect trial medication		
C1.01	Study drug medication not taken at all LABEL: Study drug medication not taken at all.		PPS, SAF
C1.02#	Patient skipped an intermediate dose without proper reason LABEL: Patient skipped an intermediate dose without proper reason.	Patient missing a dose at an intermediate visit without proper reason when dose at a later scheduled visit has been taken. Decision based on medical judgment.	PPS

Proprietary confidential information © 2021 Boehringer Ingelheim International GmbH or one or more of its affiliated companies

C1.03#	Patient skipped an intermediate dose due to COVID 19 LABEL: Patient skipped an intermediate dose due to COVID 19	Patient missing a dose at an intermediate visit when dose at a later scheduled visit has been taken due to covid-19 Decision based on medical judgment.	PPS
C2	Incorrect Dosing		
C2.01	Incorrect medication received prior to Week 12 LABEL: Incorrect dose received prior to Week 12	Randomized patient who received or miss one or more incorrect syringes of treatment not as planned at any scheduled visit prior to Week 12 Can only be finally judged after DBL since unblinding information is required	PPS
C3	Randomization not followed		
C3.01	Treated without randomisation LABEL: Treated without randomisation.	Patient treated according to eCRF, but not randomised according to IVRS.	RS, SAF, PPS
C3.02	Randomization order of stratification not followed LABEL: Stratification error	Stratification error regarding TNFi naïve and TNFi-failure Programming check and manual review after DBL	PPS
C4	Medication code broken		
C4.01	Medication code broken before week 12 inappropriately LABEL: Code broken early without valid reason.	Medication code was broken prior to DBL for no valid reason. Final decision at the DBL meeting based on medical judgment.	PPS
D	Concomitant medication		
D1	Previous medication		

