6.3 SUBJECT SETS ANALYSED

The following analysis sets will be defined for this trial:

Enrolled Set (ES)

This patient set includes all patients who signed informed consent. It will be used for analyses of patient disposition.

Randomized Set (RS):

This patient set includes all randomized patients. Treatment assignment will be as randomized.

Safety Analysis Set (SAF):

This patient set includes all patients who were randomized and received at least one dose of study drug. This is the main analysis set for efficacy and safety. Patients will be analyzed according to the actual treatment received.

Per-Protocol Set (PPS):

This patient set includes all patients in the randomized set who adhered to the CTP without any iPDs which are flagged for exclusion from the PPS in the table above. The PPS will be used for sensitivity analysis on the primary endpoint.

The discussion of all exceptional cases and problems and the decisions on the allocation of patients to populations will be made at latest at the RPM/DBLM.

Handling of Treatment Misallocations in Analysis Sets

If a patient is randomized but not treated, they will not be reported under their randomized treatment group for efficacy and safety analysis according to PPS, and SAF.

If a subject is treated but not randomized, they will be excluded from the efficacy analysis and safety analysis by definition. However, subjects under such circumstances will be described in the final clinical trial report.

If a subject is randomized but takes incorrect treatment during the study, then:

- For efficacy and safety analyses using the SAF which are based on actual treatment:
 - If a subject is planned to receive administration of Spesolimab (randomized to Speso), then they will be reported under the Spesolimab group if the subject receives at least 1 vial of randomized Spesolimab.
 - If a subject is planned to receive placebo treatment, then they will be reported under the placebo arm if they are treated and receive no vial of randomized Spesolimab. If the subject receives ≥ 1 vial of randomized Spesolimab, then the patient will be handled differently for efficacy analysis and safety analysis. It will keep as placebo for efficacy reporting. For safety, then the patient will be reported as treated with Spesolimab treatment group.

Proprietary confidential information © 2021 Boehringer Ingelheim International GmbH or one or more of its affiliated companies

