Table 6.3: 1 Overview of use of patient analysis sets by class of endpoint and handling of estimand and missing data

Class of Endpoints	ES	RS	SAF	PKS	PPS
Disposition	OR	OR			
Compliance and exposure			OR		
iPD		OR			
Demographic/baseline characteristics		OR	OR		
Concomitant medication		OR			
Primary endpoint			EC-H-MMRM EC-H-MMRM ¹ EC-H-MMRM ⁴ EC-S-MMRM ¹ OC ² , OC-IR ²		EC-H-MMRM ¹
Secondary binary efficacy endpoints			EC-H-NRI, EC-H-NRI ¹ EC-H-NRI ⁴ OC ² EC-H-MI ³		
Secondary continuous efficacy endpoints			EC-H-MMRM EC-H-MMRM ¹ EC-H-MMRM ⁴ EC-S-MMRM ³ OC ²		
Further efficacy endpoints			Binary: EC-H-NRI Continuous: EC-H-MMRM ¹ All: OC ² ,		
Concentration & ADA			OR	OR	
Safety data			OR OC-IR		

¹ sensitivity/further analysis

² descriptive display only

³ selected endpoints.

⁴ subgroup analysis

For explanation of the different approaches with regard to missing data see [Section 6.6](#).

[figure not shown]
EC-H: Hybrid strategy by implementing estimand concept. Any data post rescue medication use will be censored.

EC-S: Supplementary strategy by implementing estimand concept. Any data collected after use of any rescue therapy or restricted medication are censored.

OC = observed cases excluding values after any use of rescue medication.

OC-IR = observed cases including also values after any use of rescue medication.

OR = original results.

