7.8 SAFETY ANALYSIS

All safety analyses will be performed on the safety analysis set.

All safety analyses will be performed following BI standards. No hypothesis testing is planned. OC-IR and OR methods will be used for safety reporting. All safety analysis will be performed for on-treatment period.

AE and possibly clinically significant laboratory abnormalities will be analyzed under OR (as defined in [Section 6.6.3](#)); the safety data by visit, i.e., laboratory, vital signs and local tolerability, will be analysed under OC-IR (as defined in [Section 6.6.3](#)).

As the onset time of an AE will not be collected in the trial, any AE which occurs on the same day as a treatment dose will be assigned to the “post treatment”. For safety assessments by visits, if time is not collected, data on the same day of a treatment dose will be treated to be “prior treatment” except for scheduled local tolerability and post-dose vital signs assessments.

Off-treatment data will be listed only.

Additional analyses on AE will be also included:

AE within loading stage

Proprietary confidential information © 2021 Boehringer Ingelheim International GmbH or one or more of its affiliated companies
For AE, the additional safety tables for loading dose stage will be produced by grouping patients based on their loading doses (1200 mg, Placebo) using SAF. The outputs will include on-treatment data up to the first maintenance dose at or post week 4. If patients discontinued from treatment prior to receiving first maintenance dose, then the safety data up to the date of last loading dose + 112 days will be included.

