The frequency of patients with AEs will be summarised by treatment, primary system organ class and preferred term. AEs which were considered by the investigator to be drug related will be summarised separately. Separate tables will also be provided for patients with SAEs, patients with AESIs, patients with AE leading to discontinuation of the trial medication, and patients with other significant AEs (as described previously). AEs will also be summarized by maximum intensity.

For disclosure of AE data on ClinicalTrials.gov, the frequency of patients with non-serious AEs occurring with an incidence of greater than 5 % (in preferred terms) will be summarised by treatment, primary system organ class and preferred term. The frequency of patients with SAEs and drug related SAEs will also be summarised respectively.

For disclosure of AE data in the EudraCT register, the frequency of non-serious AEs with an incidence of greater than 5 % (in preferred terms) and the frequency of SAEs will be summarised.

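### A patient who receives study drug without being randomised is not counted in any SAF-based safety table or in the protocol-deviation summary, although the trial report would still describe the case

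*SAP*

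**What the plan says.** SAP 6.3 uses one set, the SAF, as the main set for both efficacy and safety: "This patient set includes all patients who were randomized and received at least one dose of study drug". Under the handling of treatment misallocations, the same section adds: "If a subject is treated but not randomized, they will be excluded from the efficacy analysis and safety analysis by definition". The next sentence qualifies this: "However, subjects under such circumstances will be described in the final clinical trial report".

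The deviation table in SAP 6.2 has a dedicated code, C3.01, for treatment without randomisation. Its comment reads "Patient treated according to eCRF, but not randomised according to IVRS", and it excludes the patient from RS, SAF and PPS.

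SAP 7.8 then fixes the population for safety: "All safety analyses will be performed on the safety analysis set". Table 6.3:1 places both safety data and compliance/exposure on the SAF. The iPD summary and listing are run on the RS (SAP 6.2 and Table 6.3:1).

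The protocol has the same restriction. Its Treated Set in 7.2.1 requires randomisation plus a dose, and 7.2.5 says "All randomized and treated patients will be included in the safety analysis".

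**The concern.** Randomisation protects the comparison between arms. It has no bearing on whether an event occurred after exposure. The safety analyses here are descriptive, with no testing planned, so there is little inferential reason to make randomisation a condition for being counted. The occurrence of TEAEs is the trial's defined safety endpoint, and a reader takes its frequency from the tables.

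The patients concerned would be those for whom trial procedures had already failed. At stake is whether such an exposure, and any event that follows it, enters the summary counts that readers and the registries use.

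**Working it through.** The documents give no figure for this point, so there is none to reproduce. The check is a trace of the rules, followed by a simple proportion.

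**Which outputs lose the patient**

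1. Set membership. The SAF requires randomisation and at least one dose (SAP 6.3). A treated but unrandomised patient fails the first condition, and C3.01 repeats the exclusion (SAP 6.2).
2. Safety tables. All safety analyses use the SAF (SAP 7.8). SAP 7.8.1 plans the AE tables within that framework: "Separate tables will also be provided for patients with SAEs, patients with AESIs, patients with AE leading to discontinuation of the trial medication". The ClinicalTrials.gov and EudraCT summaries are in the same section. The laboratory tables (SAP 7.8.2) and exposure (Table 6.3:1) also use the SAF. The patient is in neither the numerator nor the denominator of any of these.
3. Deviation summary. iPDs are identified for all enrolled patients but summarised and listed on the RS. C3.01 removes the patient from the RS, so the table meant to report this deviation cannot show it.
4. Disposition. The categories in SAP 7 include screened but not randomised, and randomised and treated. None covers treated without randomisation, so the patient would sit among the screened-but-not-randomised patients.

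**Which outputs keep the patient**

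- The description in the trial report (SAP 6.3).
- The individual listings, which cover all patients and name no analysis set (SAP 7, General Remarks).
- Reporting of SAEs and AESIs to the sponsor within 24 hours (Protocol 5.2.6.2.2).
- DMC review of all available unblinded safety data (Protocol 7.2.7, SAP 7.10).

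**Comparison with the neighbouring rule**

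For a patient randomised to placebo who receives at least one vial of spesolimab, SAP 6.3 keeps the patient under placebo for efficacy and reports the patient under spesolimab for safety. There the SAP already lets actual exposure govern safety when allocation goes wrong. The rule for the unrandomised patient does not follow that principle.

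**Size**

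Inputs: planned arms of 30 and 15 (protocol synopsis), and one omitted patient (assumption). If *x* of *n* counted patients have an event, including the omitted patient gives:

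- with an event: (*x* + 1)/(*n* + 1), which is at least *x*/*n*;
- without an event: *x*/(*n* + 1), which is at most *x*/*n*.

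| Omitted patient | As planned | All dosed patients counted |
|---|---|---|
| Received spesolimab, had the only event | 0/30 = 0% | 1/31 = 3.2% |
| Received placebo, had the only event | 0/15 = 0% | 1/16 = 6.3% |
| Received spesolimab, no event, one event elsewhere in the arm | 1/30 = 3.3% | 1/31 = 3.2% |

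The count of patients with events can only be understated. The percentage can be understated or slightly overstated. With no such patient, nothing changes.

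**The case against.** The strongest case on the other side has four parts.

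- **The case is unlikely.** The IRT performs the randomisation and assigns medication numbers at randomisation and at each later dosing visit (Protocol 4.1.3), and a two-person rule applies to preparation and administration (Protocol 4.1.4). Treatment without randomisation would need drug used outside that chain. C3.01 is triggered by a mismatch between eCRF and IVRS, so some hits may be data errors that the discrepancy review in SAP 6.2 would resolve. This stands. The most likely number is zero, and a code in a deviation table does not show that the event is expected.
- **The information is not discarded.** A reader might infer that the patient's events vanish from the trial. The documents do not support that, given the report description, the listings, expedited reporting and DMC review. This also stands and limits the point to the summary counts. A narrative or a listing still does not put the event into a frequency table.
- **The rule is pre-specified and agrees with the protocol.** A reader might infer that the SAP departs from the protocol. It does not, because Protocol 7.2.1 and 7.2.5 have the same restriction. The weakness is one of definition, shared by both documents.
- **Adding an unrandomised patient mixes a non-randomised case into by-arm columns.** The objective is spesolimab compared with placebo, so keeping such a patient apart is defensible. This carries limited weight, because the safety tables are descriptive and a footnote can identify the patient.

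**Conclusion.** The point holds in a narrow form. By rule, a patient dosed without randomisation is left out of every SAF-based safety table, and the deviation is left out of the iPD summary. The patient remains in the report text, in the listings and under safety oversight.

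A reader might infer that the rule biases safety in favour of spesolimab. The documents do not support this. An omitted placebo patient with an event would lower the placebo rate, and an omitted patient without an event would raise the rate in that patient's arm. Only the statement about counts is one-directional.

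The 3.2% and 6.3% are illustrations. They assume planned arm sizes, one such patient, and no other event in the arm. The documents give no expected number of such patients. The matter is minor but worth correcting, because the change is cheap and brings the rule into line with the SAP's own treatment of misallocated placebo patients.

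**What to change.** - **SAP 6.3.** Define the safety set as all patients who received at least one dose of study drug, randomised or not, by the drug actually received. Each syringe and vial has its own medication number (Protocol 4.1.3), which should allow the product to be identified. Keep randomised-and-treated as a separate efficacy set. Remove safety from the sentence that excludes treated but unrandomised subjects, and keep the description in the report.
- **SAP 6.2.** Change C3.01 to exclude from RS, the efficacy set and PPS, but not from the safety set. C1.01 (never dosed) also names the SAF and should list both new sets. Report C3.01 cases in the iPD summary even though they are outside the RS, and give them their own line in disposition.
- **SAP Table 6.3:1.** Split the SAF column into an efficacy column and a safety column.
- **Protocol 7.2.1 and 7.2.5.** Align the wording. Protocol 7.2.1 defines the PPS from the safety analysis set, so that reference should move to the efficacy set.
- **Tables.** Footnote any unrandomised patient shown in a by-arm safety table.

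The cost is wording in both documents, a second population flag and one more column in the overview table. Efficacy results do not change. The small downside is a non-randomised patient in a descriptive by-arm table, which the footnote handles.

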4. TREATMENTS

4.1 INVESTIGATIONAL TREATMENTS

4.1.1 Identity of the Investigational Medicinal Products

Table 4.1.1: 1 Test product spesolimab solution for infusion

Substance:	Spesolimab
Pharmaceutical formulation:	Solution for infusion
Source:	Boehringer Ingelheim Pharma GmbH & Co. KG
Chemical form:	Anti-human IL-36 Receptor mAb
Molecular weight:	146 kDa
Unit strength:	Spesolimab 450mg/vial (60mg/mL x 7,5mL)
Route of administration:	Intravenous infusions
Posology:	Active arm: 1200mg weekly at Weeks 0, 1 and 2 for a total loading dose of 3600mg

Table 4.1.1: 2 Test product BI matching placebo solution for infusion

Substance:	Placebo matching to spesolimab
Pharmaceutical formulation:	Solution for infusion
Source:	Boehringer Ingelheim Pharma GmbH & Co. KG
Unit strength:	Placebo to match spesolimab 450mg/vial (60mg/mL x 7,5mL)
Route of administration:	Intravenous infusions
Posology:	Placebo arm: Placebo weekly at Weeks 0, 1 and 2 matching a total loading dose of 3600mg spesolimab

Table 4.1.1: 3 Test product spesolimab solution for injection

Substance:	Spesolimab
Pharmaceutical formulation:	Solution for injection
Source:	Boehringer Ingelheim Pharma GmbH & Co. KG
Chemical form:	Anti-human IL-36 Receptor mAb
Molecular weight:	146 kDa
Unit strength:	Spesolimab 300mg/pre-filled syringe (150mg/mL x 2mL)
Route of administration:	Subcutaneous injections
Posology:	Active arm: 1200 mg every 2 weeks at Weeks 4, 6, 8 and 10

Table 4.1.1: 4 Test product BI matching placebo solution for injection

Substance:	Placebo matching to spesolimab
Pharmaceutical formulation:	Solution for injection
Source:	Boehringer Ingelheim Pharma GmbH & Co. KG
Unit strength:	Placebo to match spesolimab 300mg / Pre-filled syringe. (150mg/mL x 2mL)
Route of administration:	Subcutaneous injections
Posology:	Placebo arm: Placebo every two weeks at Weeks 4, 6, 8 and 10.

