4.1.2 Selection of doses in the trial and dose modifications

The aim of this trial (1368-0052) is to provide proof of clinical concept that spesolimab is active in treating moderate to severe hidradenitis suppurativa when compared with placebo. It will also help understanding if this benefit is clinically relevant and sufficient to grant further clinical development of spesolimab in this indication.

Patients in the active arm will receive a loading dose of 3600mg spesolimab in 3 weekly intravenous administrations of 1200mg spesolimab each (week 0 to week 2. This is 3 infusions in total for the loading dose). Patients in the placebo arm will receive matching placebo intravenous administrations at the same planned timepoints.

From week 4 to week 10 (both included) patients will receive subcutaneous injections of 1200mg spesolimab or matching placebo every two weeks (4 injections per visit for a maximum of 4 visits)

This dose/regimen was selected to optimize the exposure of spesolimab to evaluate its efficacy in hidradenitis suppurativa. The intravenous loading dose is selected to maximize the

treatment response, the duration of response, and to reach a steady state sooner. A loading dose may also allow for an earlier onset of response prior to 12 weeks. The intravenous loading dose is followed by a subcutaneous maintenance dose given every 2 weeks. This dose is the maximum subcutaneous dose that can be conveniently given based on the injection volume and number of injections.

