4.1.3 Method of assigning patients to treatment groups

An Interactive Response Technology (IRT) will be used to screen eligible patients, perform drug assignment, manage initial/re-supply ordering of drug supplies and handle emergency un-blinding. The investigator will receive all necessary instructions to access the IRT from the Sponsor. Detailed IRT functions and procedures will be documented in the user requirement specifications mutually agreed to by the sponsor and the IRT vendor.

After the assessment of all in- and exclusion criteria, each eligible patient will be randomized to receive 12 weeks of treatment with spesolimab or placebo according to a randomization plan in a 2:1 ratio at visit 2 in a blinded fashion via Interactive Response Technology (IRT). Randomization will be stratified by TNFi-naïve population versus TNFi-failure population.

At randomization as well as subsequent medication administration visits, IRT will assign medication numbers. Note that the medication number is different from the patient number (the latter is generated during screening via the IRT System). Each syringe and vial will have an individual medication number for dispensation.

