4.1.4 Drug assignment and administration of doses for each patient

Patients will be treated with spesolimab or matching placebo as indicated in the [Flowchart](#) and [section 3.1](#).

The medication will be assigned via IRT.

Patients will receive i.v. spesolimab at week 0, 1 and 2.

Detailed instructions for the preparation of the solution for infusion, the volume to be administered and the infusion rate are provided in the ISF.

Patients will receive spesolimab s.c. injections at week 4, 6, 8 and 10.

Injection site should not be close to a vein and it should avoid sites where the skin is tender, bruised, erythematous, or indurated, and should be alternated to other areas for subsequent doses.

Detailed instructions for use and handling of spesolimab syringes are provided in the ISF.

Patients have to be closely monitored for local or systemic hypersensitivity reactions for 1 hour following s.c. or i.v. study drug administration. Patients should be closely monitored for signs and symptoms of injection site or systemic hypersensitivity reactions following study drug administration. Study personnel should observe the injection site for signs of redness, swelling or hardness. They should also ask subjects about itching, dizziness or shortness of breath. Patients should be advised that if they experience redness, swelling or other changes

at the injection site, they should notify site personnel. They should further be advised that if they experience itching all over or a feeling of being swollen, dizzy or short of breath, they should seek emergency medical attention immediately and notify site personnel.

The administration of the trial medication on all applicable study days will be done under supervision of the investigating physician or a designee at the site. If available, a pharmacist should prepare the study medication. The so-called four eye principle (two-person rule) should be applied for preparation (e.g. choosing the correct vials with the correct medication number) and administration of trial medication.

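### SAP 6.3's misallocation rule counts only vials, so a placebo-randomised patient whose only spesolimab exposure was by pre-filled syringe would be reported as placebo for safety

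*SAP*

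**What the plan says.** SAP 6.3 makes the safety analysis set (SAF) the main set for efficacy and safety and analyses its patients by the treatment they actually received. A passage on treatment misallocations then covers a randomised patient who takes the wrong treatment during the study. It has two bullets, and both count vials:

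- Randomised to spesolimab: reported under spesolimab, for efficacy and safety, if at least one active vial was received.
- Randomised to placebo: "they will be reported under the placebo arm if they are treated and receive no vial of randomized Spesolimab". With one or more active vials, the patient stays placebo for efficacy and is reported under spesolimab for safety.

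Neither bullet mentions syringes.

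The protocol supplies two presentations. Section 4.1.1 lists the infusion product as "Spesolimab 450mg/vial (60mg/mL x 7,5mL" and the injection product as "Spesolimab 300mg/pre-filled syringe (150mg/mL x 2mL". Section 4.1.4 ties each to its visits: "Patients will receive i.v. spesolimab at week 0, 1 and 2" and "Patients will receive spesolimab s.c. injections at week 4, 6, 8 and 10". Section 4.1.2 gives the number of injections: "4 injections per visit for a maximum of 4 visits". Section 4.1.3 treats the two as separate dispensing units: "Each syringe and vial will have an individual medication number for dispensation".

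**The concern.** The misallocation rule exists to place patients exposed to spesolimab in the spesolimab safety column. Because it tests only for vials, it cannot detect exposure that came only through the maintenance injections. A placebo-randomised patient given active syringes by mistake, and no active vial, would keep the placebo label for safety. Adverse events after active drug would then be tabulated against placebo. The on-treatment period in SAP 6.1 can run to 112 days after the last maintenance dose, so later events could be affected too.

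A second gap follows from the same wording. A spesolimab-randomised patient who received active syringes but no active vial does not satisfy the first bullet, and no other sentence assigns a column. That bullet governs both efficacy and safety.

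The word vial is hard to read as shorthand for any unit of study drug. Protocol 4.1.3 distinguishes vials from syringes, and the SAP uses the word syringes elsewhere, in the comment to deviation code C2.01.

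**Working it through.** **Inputs.** Dose per visit 1200 mg; 450 mg vials; 300 mg syringes (Protocol 4.1.1). Three infusion visits and four injection visits (Protocol 4.1.4). Planned arms of 30 spesolimab and 15 placebo patients (Protocol synopsis).

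**Step 1: reproduce the protocol's injection count.** 1200 / 300 = 4 syringes per visit, as Protocol 4.1.2 states. Over four visits, 4 x 4 = 16 syringes. The loading dose is 3 x 1200 = 3600 mg, also as stated.

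**Step 2: what the rule does not look at.** Syringes serve 4 of 7 dosing visits and carry 4 x 1200 = 4800 mg of 7 x 1200 = 8400 mg, which is 57%. This shows that the omission covers a main part of the regimen. It does not measure how often or how badly patients would be misclassified.

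**Step 3: apply the rule case by case.** The columns show the safety group under the current text and with syringes counted.

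| Randomised to | Active vials | Active syringes | Current text | Syringes counted |
|---|---|---|---|---|
| Placebo | 0 | 0 | Placebo | Placebo |
| Placebo | 0 | 1 to 16 | **Placebo** | **Spesolimab** |
| Placebo | 1 or more | any | Spesolimab | Spesolimab |
| Spesolimab | 0 | 1 or more | **No rule** | **Spesolimab** |
| Spesolimab | 1 or more | any | Spesolimab | Spesolimab |
| Spesolimab | 0 | 0 | No rule | No rule |

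Only the two rows in bold change. For efficacy, the placebo-randomised rows are placebo throughout.

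**Step 4: effect of one misplaced placebo-randomised patient.** The patient is 1/15 = 6.7% of the planned placebo arm. Let k be the number of patients with a given event in the placebo column while it includes this patient.

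- If this patient has the event, the rate should be (k - 1)/14 instead of k/15. The difference is k/15 - (k - 1)/14 = (15 - k)/210. For k = 1 that is 14/210 = 6.7 points; for k = 3 it is 12/210 = 5.7 points.
- If this patient does not have the event, the rate should be k/14 instead of k/15, a difference of k/210. For k = 0 there is no change; for k = 3 it is 3/210 = 1.4 points.

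For an infrequent event, then, a shift near 6.7 points requires that this patient has it.

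**The case against.** The best defence is that the governing principle stands in the same section: SAF patients are analysed by the treatment actually received, and a patient injected with spesolimab has received it. On that view the bullets are loosely worded and the principle settles both gaps. SAP 6.3 also sends exceptional cases to the report planning or database lock meeting. Protocol 4.1.3 and 4.1.4 guard against the error with individually numbered units assigned by IRT and a two-person check. Safety analyses are descriptive, and individual data are listed.

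Much of this stands, and it is why the point is minor. It does not remove the defect. The principle and the detailed rule give different answers for the same patient, and an analyst is likely to program the detailed rule. The meeting is only a partial safeguard: the comment to C2.01 says incorrect medication can be finally judged only after database lock, because unblinding information is needed. SAP 6.1 labels groups by Day 1 treatment, but that does not explain the wording either. The rule in 6.3 concerns errors during the study and already reaches the infusions at Weeks 1 and 2.

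A reader might also infer that the dosing deviation has the opposite gap, because the comment to C2.01 in SAP Table 6.2:1 reads "Randomized patient who received or miss one or more incorrect syringes of treatment not as planned at any scheduled visit prior to Week 12", and so that intravenous errors stay in the per-protocol set. The documents do not support this. The description and label of the same code cover any incorrect medication or dose before Week 12, Protocol 7.2.1 counts incorrect medication as an important deviation, and SAP 6.2 allows the table to be supplemented. Only the comment is narrower than its own heading.

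**Conclusion.** The inconsistency is real and minor. Read literally, SAP 6.3 leaves a placebo-randomised patient with syringe-only spesolimab exposure in the placebo safety column, contrary to the SAF definition in that section. It also gives no column to a spesolimab-randomised patient with active syringes but no active vial.

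Three stronger readings should be avoided:

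- Not every placebo patient injected with active drug is misplaced. One who also received an active vial is moved correctly.
- Placebo-arm efficacy is not at risk, because the SAP keeps these patients as placebo for efficacy in any case.
- Neither the 57% share of the regimen nor the 6.7% is an expected distortion. The first describes the dosing schedule. The second is one patient's share of the arm, and for an infrequent event it becomes a shift of about that size only if that patient has the event.

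The conclusion assumes that a dispensing error of this kind occurs, with a frequency the documents do not give, that 15 placebo patients are treated as planned, and that the bullets are applied as written.

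**What to change.** In both bullets of SAP 6.3, wherever the rule refers to a vial, write vial or pre-filled syringe. This brings the rule into line with the SAF definition. It costs a wording change, best made before treatment information is released. No new data are needed: Protocol 4.1.3 gives every vial and syringe its own medication number, and Protocol 4.1.8 requires a record of use by each patient.

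Two optional clarifications could go in the same revision. The comment to C2.01 could name vials as well as syringes so that it matches its own description. The SAP could also state the column for a spesolimab-randomised patient who received no active unit at all, since the wording change leaves that case to the general principle.
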